14.1.3.2. Epidemiological methods

14.1.3.2.1. FREQUENCY MEASUREMENT

It is considered pertinent to carry out measures of frequency of the event of success and failure. It is intended to be addressed through the calculation of cumulative incidence (CI); all the subjects are measured in the same approximate period of time both in the exposure to the methods and if adverse reactions appear. Thus it is possible to know the probability of developing the successful event in a period of time. It will be calculated as follows: $CI = \text{No new}$

cases / population at risk This methodology could be justified because it is a prospective study, in which the time variable is not the main one, however, it is found throughout the field work.

14.1.3.2.2. ASSOCIATION MEASURE

To measure the effect of the exposure of each intervention, a measurement will be carried out through Odds-Ratio (OR).

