2.13. Subjects and sample size

Population. Adult healthy subjects.

Sample size. It is required to enroll 54 subjects with a 95% of level of confidence and 80% level of power.

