14. STATISTICAL ANALYSIS PLAN

14.1. Main analysis

14.1. 1. Definition of variables

Primary variable

Successful venipuncture at the first attempt. Dichotomous qualitative variable. Success / Failure

Secondary variables

Successful venipuncture frequency. Discrete quantitative variable. (1,2,3,4)

Visual intensity of hemolysis. Discrete quantitative variable. It is measured in stadiums.

Scale of expressed pain intensity (VAS). Discrete quantitative variable.

Scale skin types Fitzpatrick. Discrete quantitative variable.

Ingestion of liquids (less than 500 ml) in the last 6-8h prior to cannulation. Discrete quantitative variable (measured in glasses); it will be transcribed continuously for statistical analysis.

Affiliation of individuals

Respected fasting of 6-8 hours. Dichotomous qualitative variable.

Age. Quantitative variable continues.

Sex. Dichotomous qualitative variable.

Race. Discrete quantitative variable. 1 -> Caucasian 2 -> Black 3 -> Asian 4 -> Latin

BP. Continuous quantitative variable.

HR. Continuous quantitative variable.

T. Continuous quantitative variable.

BMI Continuous quantitative variable.

14.1. 2. Sample size calculation

The sample calculation is performed with the GRANMO calculator (63). It assumes a random risk (alpha) of 5% and a statistical power (beta) of 80%; for which it is tried to prove the veracity of the null hypothesis, of bilateral type.

That is, the risk of rejecting the null hypothesis when this is true is 5%, and the probability of not rejecting it being false is 20%.

In the literature, the success of peripheral intravenous canals was recorded in the first attempt, using the usual technique, in 74% of the cases (55). Currently, a proportion of peripheral intravenous cannulation has been registered at the first attempt of 73%, in an ultrasound ecoguided manner (33). In relation to the second successful attempt, in the usual clinical practice it amounts to 92% of the cases and, in the ultrasound ecoguided to 91% (33.55).

For the present work we intend to achieve a 95% success rate in antebrachial venous cannulation at the first attempt. Thus, overcome with one of the alternative methods proposed in this study the cumulative proportion of the second attempt of the usual and eco guided clinical practice.

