It is considered a clinically relevant difference the successful venous cannulation at the first attempt when, not only allows the cannulation at the first attempt of those cases that hypothetically would be observed, but accumulate to those cases that, in a way observed in the literature, the cannulation has been achieved at the second attempt, and hypothetically, that success can be achieved in the first attempt.

The comparative indicators are based on the comparison method and the reduction of intraindividual variability. It is considered a root of the experience, one of them is lost; An average of both percentages has been made, thus obtaining a 12% loss approximately.

Therefore, the calculation of the sample size should be followed through the modality of proportions, paired measures (repeated in a group). Fix in the proportion with pre-intervention event 0.74, in the proportion with post-intervention event 0.95, and the loss ratio 0.12.

Finally, the estimated sample size is 60 subjects.

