14.1.3.1.2. MULTIVARIATE STATISTICS

Therefore, it is considered pertinent to perform a logistic regression, multivariate statistics. The primary variable is assumed as the dependent variable and the secondary variables as returnable or explanatory. The primary variable fulfills the requirement of being dichotomous and the return variables assume any type of variable. It is assumed the need to create dummy variables with alternative methods, whose reference will be the comparator.

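### The odds ratio planned for each intervention has no finite estimate if that intervention has no failures; at the plan's own 95% target this has a 36–40% chance, and no fallback is given

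*Combined protocol and SAP*

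**What the plan says.** McNemar's test comes first (14.1.3.1.1). If it is significant, the plan says it must then establish which of the three methods works best. Section 14.1.3.1.2 does this by logistic regression on first-attempt success: "It is assumed the need to create dummy variables with alternative methods, whose reference will be the comparator". Section 14.1.3.2.2 fixes the measure: "To measure the effect of the exposure of each intervention, a measurement will be carried out through Odds-Ratio (OR". Section 14.3 uses the same regression for the secondary objective on the effectiveness of all methods.

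The design point is in 14.1.2: "For the present work we intend to achieve a 95% success rate in antebrachial venous cannulation at the first attempt", and for the calculation, "Fix in the proportion with pre-intervention event 0.74, in the proportion with post-intervention event 0.95, and the loss ratio 0.12". The result is "Finally, the estimated sample size is 60 subjects". The abstract (2.13) instead says "It is required to enroll 54 subjects with a 95% of level of confidence and 80% level of power", and 9.9 ends fieldwork at subject 54. Section 6.3 allocates four of every twelve envelopes to each intervention, over five blocks.

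No section names an exact, penalised or conditional model, a rule for empty cells, or an alternative measure if the odds ratio cannot be estimated.

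**The concern.** An odds ratio needs at least one failure in the arm. With about 20 subjects per intervention and a target of 95%, the plan expects about one failure per arm, so none at all is an ordinary result. The likelihood then rises without limit as the coefficient grows. Software stops at an arbitrary iteration and prints a huge odds ratio with a huge standard error.

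The problem arises when an intervention performs best. An analyst who reads the default coefficient table could see the perfect arm as the least convincing of the three, and this regression is the plan's route to naming the best method. Without a rule in the plan, the remedy would be chosen after the data are seen.

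**Working it through.** **Inputs.** Success 0.74 on the comparator and 0.95 on an intervention, loss 12%, two-sided 5%, power 80% (14.1.2). Subjects per intervention: 60/3 = 20 (6.3), or 54/3 = 18 (2.13, 9.9). Section 7.4 makes the analysis per protocol, so an arm may be smaller.

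**The plan's own figure.** The usual McNemar formula is n = [z_a·√pd + z_b·√(pd − d²)]²/d², with d = 0.21. The documents do not give the discordant proportions. Assuming cells of 0.26 and 0.05 (pd = 0.31), n = 52.8, and 52.8/0.88 = 60, which matches. Under independence (cells 0.247 and 0.037) the same formula gives 48.1, so 55.

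**Chance of no failures in one intervention, p^n.**

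| True success | n = 18 | n = 20 |
|---|---|---|
| 0.95 | 39.7% | 35.8% |
| 0.90 | 15.0% | 12.2% |
| 0.74 | 0.4% | 0.2% |

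At 0.95 with 17 or 16 analysed, it is 42% or 44%.

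**What the regression returns.** I take 14 failures in 54 comparator attempts (40/54 = 74%), no failures in 18 on one intervention and two in 18 on each of the others. After 20 Newton steps the first coefficient is 20.2 with SE 9474, odds ratio 5.7 × 10^8 and Wald p = 0.998. There is no finite maximum, so these values only reflect where the iteration stopped.

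With one failure instead, the odds ratio is (17/1)/(40/14) = 5.95, Wald p = 0.097. With 20 per arm and 44/60 on the comparator, no failures gives p = 0.998; one failure gives (19/1)/(44/16) = 6.9, p = 0.070. The better result gets the worse Wald p.

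**Same counts without Wald.** For 18/18 against 40/54 the likelihood-ratio p is 0.0025, and the profile-likelihood 95% lower limit for the odds ratio is 2.85. For 20/20 against 44/60 they are 0.0012 and 3.34. These figures ignore the pairing and serve only to show that usable information remains.

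**Other forms of the odds ratio.** A crude 2×2 odds ratio is infinite in the same cases. A matched-pair odds ratio is infinite when no subject succeeds on the comparator and fails on the intervention. If attempts are independent that cell is 0.74 × 0.05 = 0.037, so the chance is 0.963^18 = 51% or 0.963^20 = 47%.

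**Room for covariates.** If all three interventions reach 95%, expected failures in 54 subjects are 54 × 0.26 + 54 × 0.05 = 16.7 over both periods. That supports few terms beyond the three method dummies.

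**The case against.** The strongest reply is that much of the plan survives an empty cell. Section 14.1.3.2.1 reports success as cumulative incidence, which is well defined at 18/18. Section 10.2.1 judges effectiveness by a success rate above 74%, which a perfect arm meets. McNemar's test is untouched. The plan never mentions the Wald test, and a likelihood-ratio test on the same counts is clearly significant. All of this stands. A reader might infer that a perfect arm leaves the main objective with nothing defined, or that it must come out non-significant; the documents support neither.

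Two other stronger readings also fail. If all three interventions were truly at 95%, at least one would have no failures in 74–78% of trials (1 − (1 − 0.358)³ to 1 − (1 − 0.397)³), but 14.1.2 aims for 95% with one of the methods. And Fisher's exact p of 0.015 for 18/18 against 40/54 should not be set against the Wald p as the answer lost: it ignores pairing, since those 18 subjects are also among the 54.

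A paired test is no easy rescue. With 18/18 and 26% comparator failure, 18 × 0.26 = 4.7 discordant pairs are expected. Exact McNemar gives p = 2 × 0.5^5 = 0.0625 at 5–0 and 0.031 at 6–0. Six or more discordant pairs occur in about 32% of such arms (42% for 20/20).

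What remains is that proportions alone give no comparison or interval for each intervention. The measure chosen for that purpose has no fallback.

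**Conclusion.** The concern holds for the per-intervention odds ratio and for any ranking of the methods drawn from it. It does not extend to the overall test, the success proportions or the effectiveness criterion.

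The 36–40% applies to one intervention whose true success is 95%, with 18 to 20 subjects analysed. It falls to 12–15% at 90% and is negligible at 74%. The infinite estimate needs no assumption about the test. The Wald p near 1 assumes that default output is used, which the plan neither requires nor rules out. Section 14.1.3.2.2 does not say which model yields the odds ratio, but the crude and matched-pair versions fail as well.

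That the odds ratio looks larger than a risk ratio or difference is a matter of reporting preference, not a reason to remove it.

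**What to change.** In 14.1.3.2.2, add for each intervention the paired difference in first-attempt success against the same subjects' comparator attempt, with a paired 95% confidence interval (Tango or Newcombe). It is defined whatever the counts.

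In 14.1.3.1.2, keep the odds ratio but obtain it by a method that tolerates empty cells and respects the pairing: exact or penalised conditional logistic regression. State that intervals and tests will be exact or profile-likelihood, not Wald. Ordinary penalised logistic regression is not enough, because it ignores that each subject contributes two attempts. Limit the model to the method terms and a few prespecified baseline covariates.

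No extra subjects or data are needed. The cost is SAP wording and, if SPSS v23 (named in 9.9) lacks these methods, another package. The downsides should be stated in the plan: penalised odds ratios are shrunk, fewer covariates are fitted, and per-intervention paired tests have low power, about 17% with 18 and 23% with 20 subjects at 0.74 against 0.95 if attempts are independent. The per-intervention results should therefore be read as estimates with intervals.

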14.2. Secondary principal analysis

14.2.1. Definition of variables

The main secondary variable is established:

Intensity of visual hemolysis. Discrete quantitative variable. It is measured in stadiums.

It aims to carry out the following secondary objective: Design and validate a visual scale of hemolysis.

To carry out its approach, through statistical methods, the following secondary variables are defined:

- o Absorbance of free hemoglobin in plasma. Continuous quantitative variable. It is measured in decimals.
- o Stadiums. Continuous quantitative variable. It is measured in absorbance ranges.
- o RGB colorimetry. Discrete quantitative variable. It is measured with whole numerical codes.
- o CMYK colorimetry. Continuous qualitative variable. It is measured in continuous percentage.
- o Blood samples. Discrete quantitative variable.
- o Observers Discrete quantitative variable.

The following variable is defined independently, since it will not be measured or used in the statistical analysis:

- Concentration of free hemoglobin in plasma. Continuous quantitative variable. It is measured in mg / dl.

However, it is considered an implicit variable in the scale on which the project is based (29) to carry out the modification of this and, therefore, the design of a new scale.

14.2.2. Statistical power and calculation of sample size

The choice of this secondary variable could be justified as the main one due to its statistical power, in relation to the sample size calculation, in order to conclude with a statistical

significance. That is, the sample size calculated for this variable could be included in the sample size calculated for the main variable; using the same fieldwork

According to a study (52) at a cutoff point for evaluation of free hemoglobin in plasma through absorbances and visual detection, the following is stated: of fifteen samples detected with absorbances, eight of them were not detected visually. That is, the visual inspection shows a predictive positive values (PPV) of 46.6%. It is tried to prove the veracity of this assumption and for it the following verification of hypothesis, of bilateral type is proposed:

H0: The positive prediction of intensity of hemolysis through visual stages is not optimal.

H1: The positive prediction of intensity of hemolysis through visual stages is optimal.

A calculation of GRANMO samples (63) has been carried out in the modality of proportions observed with respect to a reference. With an alpha error of 5% and a power of 1%, bilateral test. The reference proportion is 0.466 (52) and the objective is to reach a positive prediction of at least 0.80; It is considered optimal to detect the intensity of hemolysis in each stage. Therefore, the minimum difference to be detected is obtained through the objective of 0.80 - 0.466, that is, 0.334. Finally, it is obtained that at least 41 individuals are needed or, what is the same, 49 blood samples with a predicted proportion of losses of 20%; corresponds to possible samples with insufficient blood content for inspection.

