14.2.3. Scale design

14.2.3.1. Description

1. It will be based on a scale previously prepared (29). This will give support to the reference colorimetry and the cut points on which establish stages. The cut-off points, measured in concentrations (mg / dl), are considered as clinical relevance valued by a panel of experts(30,54).
2. The EDTA sample will be processed. Subsequently, 1 ml of the plasma of each sample is transferred to aliquots. The photograph of said aliquot will be made.
3. The absorbance of hemolysis will be analyzed. Six microliters of the plasma will be collected; because of the need for three repeated measurements.
4. The specific color of each sample (29) will be identified through the Photoshop software.

At least two design versions will be developed, based on visual colorimetry aspects.

It excludes jaundice for being healthy subjects, and try to reduce lipemia through strategically programmed blood extractions, as it appears in section 9.7.3.

In the first instance, the samples of the first period will be used for the design of the scale, and those of the second period for the validation process.

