14.2.3.3.2. Validity analysis

A. VALIDITY OF APPEARANCE.

To address the convenience of stages, it has been based on literature; They are considered experts in the subject. It will be reflected in section 14.2.3.

B. VALIDITY OF CONTENT.

We intend to evaluate if the items represent those that we want to measure, that is, increase in intensity of hemolysis. A correlation between visual stages and intensity scores could be used. assessed in 14.2.1.2. B.

B. VALIDITY OF CRITERIA.

We intend to evaluate the concordance between the measures by absorbances and those made by the observers. It is intended to calculate sensitivity, specificity, positives and negatives values of the visual inspection.

C. CONSTRUCT VALIDITY.

A possible convergence or divergence of versions one and two will be assessed. In the case of finding a convergence between two of scales, the one that higher value of concordances will be the one that will be used for the verification of hypothesis.

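### The reference 0.466 in section 14.2.2 is a sensitivity, not a PPV, and the 41 it yields counts absorbance-positive samples, not individuals

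*Combined protocol and SAP*

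**What the plan says.** Section 14.2.2 takes its reference from a cited comparison of absorbance with visual detection: "of fifteen samples detected with absorbances, eight of them were not detected visually". It then concludes: "That is, the visual inspection shows a predictive positive values (PPV) of 46.6" per cent. H0 and H1 are worded as whether positive prediction by visual stages is optimal. The reference is 0.466, the target at least 0.80 and the difference 0.334.

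The error rates are given as "With an alpha error of 5% and a power of 1%, bilateral test". The result is "at least 41 individuals are needed or, what is the same, 49 blood samples with a predicted proportion of losses of 20" per cent, and the losses are attributed to samples with too little blood. The section justifies haemolysis as the main secondary variable because "the sample size calculated for this variable could be included in the sample size calculated for the main variable".

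Four other places bear on this:
- Section 14.2.1 defines the stages as absorbance bands ("It is measured in absorbance ranges").
- Section 14.2.3.1 assigns first-period samples to designing the scale "and those of the second period for the validation process".
- Table 3 in section 9.7.3 lists three blood samples per subject in each period.
- Section 14.2.3.3.2 compares the observers with absorbance and lists sensitivity separately from the predictive values: "It is intended to calculate sensitivity, specificity, positives and negatives values of the visual inspection".

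**The concern.** A sensitivity is conditional on the reference standard being positive; a PPV is conditional on the visual reading being positive. The plan's 15 samples are defined by absorbance, so the data give the first and the text names the second. The plan does not say which denominator the hypothesis test will use.

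If the analyst repeats the calculation in 14.2.2 (visually detected among absorbance-detected), the test is sound under the wrong name. If the analyst computes a PPV in the usual way, it is set against a sensitivity. The scale could then be declared optimal while still missing 8 of 15 haemolysed samples.

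The same slip affects the unit of the sample size. The 41 is the denominator of the tested proportion. The text treats it as individuals and as samples, and allows only for insufficient volume, not for samples without haemolysis. The claim that this sample size fits inside the main one therefore has not been shown.

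**Working it through.** **Inputs.** From 14.2.2: 15 absorbance-detected samples, 8 missed visually; p0 = 0.466; p1 = 0.80; two-sided alpha 5%; 20% losses. From 14.1.2: 60 subjects and 12% losses. From Table 3: three samples per subject per period. Specificity and prevalence of absorbance-positive samples are not given, so they are assumed and shown as ranges.

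**1. The reference.** Detected visually: 15 − 8 = 7. 7/15 = 0.467 = P(visual positive | absorbance positive), which is sensitivity. PPV = 7/(number visually positive), and the plan does not give that number.

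**2. The plan's 41.** One-sample proportion with null variance:

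n = (z₀.₉₇₅ + z₀.₉₉)² × p0(1 − p0)/(p1 − p0)² = (1.960 + 2.326)² × 0.466 × 0.534/0.334² = 40.98, so 41.

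This reproduces the plan's figure at 99% power. A literal 1% power in the same formula gives 0.3.

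**3. The 49.** 41 × 1.2 = 49.2. But 49 × 0.8 = 39.2, so about 39 would remain. To keep 41 after 20% losses: 41/0.8 = 51.25, so 52. Exact power is 0.994 with 39 and 0.996 with 41, so the difference is negligible.

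**4. PPV with detection unchanged.** PPV = Se × π/[Se × π + (1 − Sp)(1 − π)], with Se = 7/15:

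| Assumed specificity | Assumed prevalence | PPV |
|---|---|---|
| 90% | 10% | 0.34 |
| 95% | 30% | 0.140/(0.140 + 0.035) = 0.80 |
| 99% | 50% | 0.98 |

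**5. Power by number of positives.** Exact binomial test, 0.466 against 0.80, 2.5% in each tail: 0.996 with 41 positives, 0.80 with 20, 0.56 with 12.

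**6. What the second period can supply.** 60 × 0.88 × 3 × 0.8 = 126.7, about 127 usable samples if all are read. Prevalence needed for 41 positives: 41/126.7 = 32.4%. For 20 positives: 20/126.7 = 15.8%.

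Taking the number of positives as Binomial(127, prevalence) and averaging the exact power over it:

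| Assumed prevalence | Averaged power |
|---|---|
| 10% | 0.58 |
| 20% | 0.91 |
| 30% | 0.99 |

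These powers treat samples as independent. Positively correlated samples from one subject would give less.

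**The case against.** **The trial may well have enough positives.** This stands. With three second-period samples per subject, the sample size can fit even though individuals, samples and positives are different counts. A reader might infer that the fit fails, or that it needs the three counts to be equal. The documents do not support that; the fit depends on an unstated prevalence. Nor do they support the poor power that would follow from taking just 41 unselected samples. The plan specifies no such set, and section 14.2.3.3.1 has observers score strategically chosen samples for inter-observer reliability.

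**The target may be staged, not binary.** Section 14.2.2 speaks of detecting intensity in each stage, and the stages are absorbance ranges. If success means assigning the correct stage, every sample enters the denominator. This ambiguity is real, so one threshold should not be imposed without reconciling it. It does not rescue the 0.466, which comes from a detected/not-detected comparison. Section 10.2.3 also already refers to a 25 mg/dl cut-off and its corresponding absorbance.

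**The two misprints are minor.** This also stands. The power figure is a slip between power and beta (section 14.1.2 similarly writes power as beta), and 49 against 52 changes almost nothing.

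**Sensitivity will be reported anyway.** True, under section 14.2.3.3.2. But that does not settle which proportion H0 and H1 test.

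**Conclusion.** The point holds as one of label and unit. The 0.466 is a sensitivity, no PPV can be obtained from the figures given, and the 41 tied to that reference is a number of absorbance-positive samples. The 41 itself is not an arithmetic error: it reproduces at 99% power.

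The size of the problem depends on quantities the documents leave open. If a PPV is tested, the 0.80 target can be met with no gain in detection at plausible but assumed values (specificity 95%, prevalence 30%). If sensitivity is tested on the full second-period pool of about 127, power is about 0.58 at 10% prevalence and 0.91 at 20%, assuming independent samples. The stated 99% is therefore conditional on obtaining 41 positives.

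A reader might go further and doubt the trial's main result or the comparison of haemolysis between methods. The documents do not support that. The primary endpoint has its own calculation, and the ANOVA in section 14.3 does not use this proportion. The scope is the validation of a secondary scale. The change is worth making because it settles the test before the data are seen.

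**What to change.** In section 14.2.2:
- Rename the tested proportion as the sensitivity of the visual scale against absorbance (0.466 against 0.80), and reword H0 and H1 to match.
- Define the 41 as absorbance-positive validation samples, and delete the wording that equates individuals with blood samples.
- State that 99% power is conditional on 41 such samples. Report the number obtained and the precision achieved.
- State, before the validation readings, which absorbance cut-off defines a positive. Reconcile it with the stages in 14.2.1, the stage-by-stage aim in 14.2.2 and the cut-off in 10.2.3.
- Keep PPV, NPV and specificity as descriptive measures, as listed in 14.2.3.3.2.
- Correct the power to 99% (beta 1%) and 49 to 52.

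The cost is rewording and two corrected figures, with no additional blood draws. The drawback is that the number of positives is unknown in advance, so the power achieved may fall below 99%; about 20 independent positives would still give about 80%.

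### The haemolysis-scale test is set against 0.466, but its alternative hypothesis claims a positive prediction that is optimal, a label tied to at least 0.80; no criterion at 0.80 is stated

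*Combined protocol and SAP*

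**What the plan says.** Section 14.2.2 gives the main secondary variable, visual intensity of haemolysis, its own hypotheses and sample size.

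- Null: "H0: The positive prediction of intensity of hemolysis through visual stages is not optimal".
- Alternative: "H1: The positive prediction of intensity of hemolysis through visual stages is optimal".
- Type of calculation: "in the modality of proportions observed with respect to a reference".
- Error rates: "With an alpha error of 5% and a power of 1%, bilateral test".
- Reference and target: "The reference proportion is 0.466 (52) and the objective is to reach a positive prediction of at least 0.80". The text then adds, of that level, "It is considered optimal to detect the intensity of hemolysis in each stage".
- Effect size: "the minimum difference to be detected is obtained through the objective of 0.80 - 0.466, that is, 0.334".
- Origin of the reference: "of fifteen samples detected with absorbances, eight of them were not detected visually", which leaves 7 of 15.

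The result is 41, raised to 49 blood samples for 20% losses.

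The validation sections add no decision rule. Section 14.2.3.3.1 plans kappa for each stage and version. Section 14.2.3.3.2 plans sensitivity, specificity and predictive values, and says that the version with the higher concordance will be used to verify the hypothesis. Neither gives a threshold for accepting the alternative.

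**The concern.** A test supports a claim about the value it is set against. Here that value is 0.466. The 0.80 enters only as the alternative used for sizing, through the difference of 0.334. Choosing a target as the planning alternative is normal practice. The fault is that the alternative hypothesis is worded as if rejection showed that the target had been reached.

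At stake is the conclusion of the designated main secondary analysis. Design and validation of the scale is a stated objective in section 5.2.2, and section 14.3 then compares haemolysis intensity between the venipuncture methods. An optimal label that rests only on beating 0.466 would lend those comparisons more authority than the data give.

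**Working it through.** **1. Reproduce the plan's figure.** Inputs from section 14.2.2: p0 = 0.466, p1 = 0.80, two-sided alpha 5%. The stated power of 1% is workable only as beta = 1%, that is, power 99%; taken literally it gives about one sample.

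n = (z0.975 + z0.99)² × p0(1 − p0) / (p1 − p0)²
= (1.960 + 2.326)² × 0.466 × 0.534 / 0.334²
= 18.37 × 0.2488 / 0.1116 = 40.98, rounded up to 41.

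The stated 41 comes out with 0.466 as the null value and 0.80 as the planning alternative. For losses, 41 × 1.2 = 49.2, which is the stated 49.

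**2. Find the upper rejection boundary.** Assume one pooled binomial count and the exact two-sided test of 0.466 at 5%. The z-test gives the same boundaries.

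| n | Smallest rejecting count | Proportion | 95% Wilson | 95% Clopper-Pearson |
|---|---|---|---|---|
| 41 | 26 | 63.4% | 48.1% to 76.4% | 46.9% to 77.9% |
| 49 | 30 | 61.2% | 47.2% to 73.6% | 46.2% to 74.8% |

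At the boundary the whole interval lies below 0.80. Data that speak against 0.80 would thus reject the null.

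**3. Chance of an upward rejection when the true value is below 0.80.** Exact binomial upper tail, P(X ≥ 26) or P(X ≥ 30):

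| True value | n = 41 | n = 49 |
|---|---|---|
| 0.60 | 39% | 49% |
| 0.65 | 65% | 76% |
| 0.70 | 86% | 93% |
| 0.75 | 97% | 99% |

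The true values are assumptions, chosen to span the gap between 0.466 and 0.80. More samples make rejection below 0.80 more likely, because the test is then more sensitive to any excess over 0.466.

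**4. Dependence on the denominator.** A positive predictive value counts only visually positive samples, and the plan gives no expected number of these. If there were 20 (an assumption), the boundary would be 14 of 20 (70%), and the chance of rejection 25% at a true 0.60 and 61% at 0.70.

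**5. Criteria that do refer to 0.80, at n = 41.**

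| Rule | Count needed | Chance of meeting it, by true value |
|---|---|---|
| Observed value at least 0.80 (0.466 is then rejected too, as 33 exceeds 26) | 33 (80.5%) | 0.70: 9%; 0.75: 27%; 0.80: 56%; 0.90: 98% |
| Lower 95% limit at least 0.80 (Wilson and Clopper-Pearson agree) | 38 (92.7%) | 0.80: 2%; 0.90: 40%; 0.95: 85% |

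**The case against.** The strongest reply is that the plan never says in words that rejecting 0.466 proves optimality. It names no test statistic, and 0.466, alpha and the two-sided setting all stand in a sample-size paragraph. The stated objective of reaching at least 0.80 could itself be the success criterion, with 0.466 used only for sizing. On that reading 33 of 41 is needed and the risk is far smaller: 9% at a true 0.70 and 27% at 0.75. This stands in part. The decision rule is inferred. But the plan has hypotheses labelled not optimal and optimal, one reference value and no other rule, so the inference is the natural one. If another rule is intended, it is unwritten.

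Second, the trial may not analyse one pooled count of 41. The plan expects 49 samples, section 14.2.3.1 assigns second-period samples to validation, and Table 3 lists three samples per subject in that period. The optimal level is also linked to detection in each stage. This stands: the probabilities are conditional.

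Third, the planned predictive values would let a reader set the estimate beside 0.80. True, but no section says that this comparison governs the conclusion.

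A reader might infer that the trial is bound to endorse a scale that misses its own standard, or that the plan requires a lower confidence limit of 0.80. The documents support neither. The first treats an inferred rule and one sample size as fixed. The second goes beyond the stated objective, and would call a scale truly at 0.80 optimal only 2% of the time.

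**Conclusion.** The point holds: as written, rejection of 0.466 does not support the stated alternative hypothesis, and nothing else in the plan ties the optimal conclusion to 0.80. A scale below 0.80 could be declared optimal. The size rests on three assumptions: that rejection leads to the optimal label, that the analysis is a single pooled binomial, and that n is 41 or 49. Under these, an observed 61% to 63% would be enough, and a scale truly at 0.70 would pass 86% to 93% of the time. A different denominator or an analysis by stage would move these figures but would not remove the mismatch between test and claim. The matter concerns the conclusion of the main secondary objective. The primary endpoint and its McNemar test are untouched.

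**What to change.** In section 14.2.2, restate the null and alternative as positive prediction not exceeding and exceeding 0.466, and word the conclusion the same way. The 41 still fits this test. Report the estimate with its 95% interval beside 0.80, and do not conclude optimal from the test alone. State the denominator, and whether the analysis is pooled or by stage.

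If the sponsor wishes to keep the optimal label, the SAP should fix a criterion tied to 0.80 before the data are seen. One option is rejection of 0.466 plus an observed value of at least 0.80. A stricter, optional one is a lower 95% limit of at least 0.80. The counts and chances for both are in the working.

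The restatement costs only SAP wording and needs no new samples. The downside of either criterion is that optimal will be claimed less often. The stricter rule has little power at 41 unless the true value is well above 0.80. By the normal approximation, a two-sided 5% test of 0.80 with 80% power needs about 108 samples if the truth is 0.90 and about 42 if it is 0.95; both true values are assumptions.
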